7. Employees of the researcher	Included/Allowed to Participate

8. Students of the researcher	Included/Allowed to Participate
9. Undervalued or disenfranchised social group	Included/Allowed to Participate
10. Active members of the military (service members), DoD personnel (including civilian employees)	Included/Allowed to Participate
11. Individual or group that is approached for participation in research during a stressful situation such as emergency room setting, childbirth (labor), etc.	Targeted Population
12. Individual or group that is disadvantaged in the distribution of social goods and services such as income, housing, transportation, or healthcare.	Included/Allowed to Participate
13. Individual or group with a serious health condition for which there are no satisfactory standard treatments.	Included/Allowed to Participate
15. Individual or group with a fear of negative consequences for not participating in the research (e.g., institutionalization, deportation, disclosure of stigmatizing behavior).	Included/Allowed to Participate
16. Any other circumstance/dynamic that could increase vulnerability to coercion or exploitation that might influence consent to research or decision to continue in research.	Included/Allowed to Participate

10.1 Additional Safeguards: A data safety and monitoring board (DSMB) and an independent medical monitor, specifically Presently, **an independent medical monitor IMM** will monitor the research procedures and the safety of the participants. Please see the attached data safety and monitoring plan (DSMP) uploaded in ETHOS.

Please note that regarding Table 9 Vulnerable Populations: The following assurances apply to all of them, they will be informed of the risks and benefits of the research, their information will be kept confidential, and they will have freedom to decline and withdraw from the research at any point. Their inclusion and participation will be subject to the monitoring by a DSMB and an IMM. The inclusion of adults lacking capacity to consent and/or adults with diminished capacity to consent, members of the military or disadvantaged individuals is made to provide for assurances regarding the participant's parents. While parents are not the focus of the research, they will be asked to complete questionnaires about themselves and about their offspring.

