14.1 Withdrawal Circumstances:

1st High risks of imminent suicide attempts, with intent, a plan and/or other conditions for study enrollment are not met. Participants can re-enroll in the study after hospitalization and/or increased levels of care in outpatient treatment and/or environmental changes (e.g., changes in school or place of residence) that leads to demonstrable stabilization and/or decrease high acute/chronic suicide risks. To re-enroll the **PI and the IMM (with possible third opinion of Pediatric Psychiatrist if needed)** must agree on the results of the study enrollment/re-enrollment conditions.

2nd Onset of significant psychotic symptoms that clearly impair judgment and ability to assent (e.g., presence of pervasive psychotic mood, visual or auditory hallucinations or other manifestations of disorganized thoughts and judgement). Note: mild, transient psychotic symptoms are allowed within the context of a depressive episode or other diagnostic category, if they do not impair the participant's ability to assent or meet criteria for a full psychotic episode as defined by the K-SADS.

3rd Onset of neurological or metabolic illness known to significantly affect brain function and structure.

4th Onset of substance dependency disorder or new evidence that symptoms are linked to substance use.

5th Onset of claustrophobia resulting in intense discomfort in the scanner that cannot be assuaged with brief anxiety decreasing interventions (e.g., talking to the experimenter/breathing and increasing verbal contact with experimenters between pulses of the scanner).

6th Known or strongly suspected SARS-COVID-2 diagnosis in the family or household or recent (1-3 days) onset of symptoms linked to a contagious illness.

7th Medication related toxicity will result in temporary withdrawal until stabilization of symptoms is ascertained via K-SADS guided assessments and/or improvement is ascertained by their attending physician.

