16.1 Foreseeable Risks

1. **Suicide attempt or completion risk.** Because the focus of this study is an intervention for **participants with recent suicide attempts and current suicide ideation**, the participants are at increased risk for suicide attempts, increased suicide thoughts and hospitalizations. **Participants who have attempted suicide are more likely to repeat attempts, to be hospitalized or to complete suicide compared to the general population of psychiatric patients. It is highly likely that the present study will entail reporting suicide attempts, suicide completions and hospitalizations given the population we are studying. Suicide attempts, completions or hospitalizations are thus a characteristic of the population and not a likely consequence of the proposed intervention which is of minimal risk and intrusiveness.**

2. In person suicide risk will be assessed at baseline and at the post-intervention assessment and additional precautions will be taken to help ensure participant safety. The PI ([name], PhD, L.P.) will work in conjunction with a designated pediatric psychiatrist at the Department of Psychiatry Child and Adolescent Clinic. [name] or the designated pediatric psychiatrist (if the PI is on vacation or in a conference) will be available to the PI and study staff during each of the clinical assessments, to consult with the study staff regarding the suicide risk, triage, and intervention planning. In addition to these resources, the UMN outpatient clinic has a list of 6 qualified providers that experimenters can call in case of emergency. During in-person assessments, if a 72-hour hold is warranted to ensure participants safety, security personnel are readily available in case experimenters determine that there is urgent need for escorting participants and families to the emergency department (ED) for possible hospitalization and/or further evaluation.

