Data Collection. Participants will complete study procedures in several appointments in person or **via remote research**. During these sessions, the subjects will be closely monitored by study staff for any indication of compromised safety for the subject (See Figure 1). Participants will also be monitored for whether they are putting effort into study procedures. Following each session, participants will complete a brief volunteer online survey regarding their experience including any discomfort during the session or any mood or behavior change since their last session. Study staff will review these and notify the PIs if there are any concerning developments. The **PIs and the IMM, with the possible alternative of the pediatric psychiatrist**, will review the information gathered during in-person or **via remote research assessments** and determine if further evaluation or action needs to be taken. Participants will complete study procedures in several appointments/**remote visits**. After data collection occurs, data will be reviewed for accuracy and completeness by the individual who gathered the data or by a similarly trained staff member or student. After data are processed and entered, they will be reviewed statistically to ensure errant outliers are minimized. Data will be captured both electronically and in paper formats and in whatever format facilitates coding reliability, training, and consistency across personnel.

We plan to manage data in the following manner for all participants recruited from University of Minnesota sources. Each participant will be assigned a random, unique identification number. This ID number will be used on all files throughout the database. The participant identification number, rather than participant names, will be placed on all forms to preserve confidentiality. The forms will be reviewed for completeness and accuracy prior to data entry. The data entry modules will be designed to accept only the valid range of values for each variable to reduce risk of the entry of erroneous values. Although every effort will be made to keep research records private, there may be times when federal or state law requires the disclosure of such records, including personal information. This is very unlikely, but if disclosure is ever required, the University of Minnesota will take steps allowable by law to protect the privacy of personal information.

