Reporting. Any unexpected adverse events, and unexpected problems that involve risk to the participants or others, or breaches of confidentiality, will be documented as per indicated in the Good Clinical Practices Standards and reported by all research staff to the PI, who will determine the next steps including coordination of response with the IMM or the pediatric psychiatrist. After been informed by any study personnel or directly becoming aware of SAE's or AE's, the PI will report any unexpected serious adverse events (SAEs) or adverse events (AEs) or unanticipated problems (UPs) involving risks to participants to the IMM or the Pediatric Psychiatrist and work with either of them to determine its severity and attribution. After consulting with the IMM or the Pediatric Psychiatrist, with aid of study coordinators –SC-, the PI will email a signed form regarding the event to the **IRB** and to the assigned national institute of mental health (**NIMH**) program officer (PO), the **DSMB** with copy to the **IMM** regarding the AE or SAE. See **Figure 2** for the flow of information and decision making.

[figure not shown]

Figure 2

Documentation to be submitted for reportable events will include the following: 1) Brief identifying information for the research protocol, 2) the date or approximate timeframe that the event occurred on and the date the PI became aware of event, 3) a description of the event and impact to the participant, 4) a description of measures taken in response (if any), 5) Confirmation monitoring entities and regulatory bodies were notified as proposed, 6) Attribution of the event/events, specifically linked or not to study or protocol procedures, 7) a description of corrective actions and changes to the protocol that have either been made or proposed if the event can be reasonably attributed to protocol or study procedures.

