Timeframe for Reporting. The PI will report to the IRB and the assigned NIMH PO within the following timeframe: (1) IRB/IMM/DSMB suspensions or terminations (within **3 business days**), (2) deaths related to study participation (within **5 business days**), (3) unexpected serious adverse events (within **7 business days**) (<https://www.nimh.nih.gov/funding/clinical-research/nimh-guidance-on-risk-based-monitoring.shtml>), (4) unanticipated problems involving risks to participants or others (within **10 business days**), (5) serious or continuing noncompliance (within **10 business days**), (6) **adverse events deemed expected or unrelated to the study (with annual progress report)**, and (7) protocol deviations that do not affect the scientific soundness of the research plans or the rights, safety or welfare of the human subjects (with annual progress report) (<https://www.nimh.nih.gov/funding/clinical-research/nimh-reportable-events-policy.shtml>).

ClinicalTrials.gov Requirements. The study will be registered with *ClinicalTrials.gov* prior to the enrollment of the first subject.

22. Provisions to Protect the Privacy Interests of Participants

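### The PI may settle an event's severity and attribution with a pediatric psychiatrist who works alongside the PI, so no independent person is required when that judgement is made

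*Combined protocol and SAP*

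**What the plan says.** Section 10.1 (Additional Safeguards) presents the IMM as one of the study's protections: an independent medical monitor who "will monitor the research procedures and the safety of the participants".

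Section 21.1 (Reporting) describes what happens when staff or the PI learn of an event. The PI brings it "to the IMM or the Pediatric Psychiatrist and work with either of them to determine its severity and attribution". The next sentence repeats the choice: "After consulting with the IMM or the Pediatric Psychiatrist", the PI sends a signed form to the IRB, the NIMH program officer and the DSMB, with a copy to the IMM.

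Section 16.1 describes the psychiatrist's place in the study. The PI "will work in conjunction with a designated pediatric psychiatrist at the Department of Psychiatry Child and Adolescent Clinic", and a named individual "or the designated pediatric psychiatrist (if the PI is on vacation or in a conference) will be available to the PI and study staff" during clinical assessments. Section 16.4 makes the designated psychiatrist a person to consult when in doubt, and one of those who may increase contact with a participant's family.

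Section 14.1 sets a different rule for re-enrolment after withdrawal. Those who must agree are the "PI and the IMM (with possible third opinion of Pediatric Psychiatrist if needed").

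Section 21.1 (Timeframe for Reporting) gives the clocks to the IRB and NIMH: item (2), related deaths, 5 business days; item (3), unexpected serious adverse events (SAEs), 7; item (4), unanticipated problems, 10. Item (6) is "adverse events deemed expected or unrelated to the study (with annual progress report").

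**The concern.** The judgement on whether an event is linked to the study is one that a sponsor normally wants an independent person to share. The plan has such a person and then makes that person optional. On the psychiatrist branch the decision can rest with the PI and a clinician who may have helped the PI assess the same participant's risk.

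The plan's advance position on attribution makes this more than formal. Section 16.1 says that reports of suicide attempts, completions and hospitalizations are highly likely, and describes these events as a feature of the population and not a probable result of the intervention. Section 21.1 says much the same in its monitoring and DSMB paragraphs. Where the protocol already leans towards unrelated, an independent view at the time of judgement has the most value. At stake is whether some events, deaths above all, reach the IRB and NIMH within days or only with the annual report.

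**Working it through.** No arithmetic beyond comparing time limits applies. The check follows the decision path through the sections.

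**Who decides.** Section 21.1 (Reporting) names the PI plus one of two people, and says so twice. Either is sufficient.

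**Who is independent.** Section 10.1 calls the IMM independent. No visible section says this of the pediatric psychiatrist. Sections 16.1 and 16.4 place that person beside the PI in risk assessment and triage. That this is a study-team role is an inference from those sections; the documents do not use the label.

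**Which clocks depend on attribution.** Item (2) requires a related death. Item (3) requires a serious and unexpected event and says nothing of relatedness. Item (4) requires an unanticipated problem, which section 21.1 (Definition of Events) limits to events that are unexpected, related or possibly related, and suggestive of more risk than was known. Item (6) takes what is deemed expected or unrelated. Applying the most specific item where two fit, which is an assumption:

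| Event | Judged related | Judged unrelated |
|---|---|---|
| Death, treated as expected | (2): 5 business days | (6): annual report |
| Death, unexpected | (2): 5 business days | (3): 7 business days, but (6) also fits |
| Other unexpected SAE | (3): 7 business days | (3): 7 business days, but (6) also fits |
| Unexpected, non-serious, suggests new risk | (4): 10 business days | (6): annual report |
| Non-fatal SAE, treated as expected | (6): annual report | (6): annual report |

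Attribution moves the first and fourth rows from days to the annual report. In the second row it costs 7 − 5 = 2 business days if item (3) governs. In the third it changes nothing unless item (6) is read to override item (3), and the text does not say which prevails. In the last row expectedness alone settles the route.

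**Whether the either/or reaches the first row.** The Reporting sentence opens with unexpected serious events and then lists adverse events and unanticipated problems. If it covers an event treated as expected, the either/or applies. If it does not, the section names nobody besides the PI to attribute that event. On both readings no independent person is required.

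**What comes afterwards.** The signed form, which must state attribution, goes to the IRB, NIMH and DSMB with a copy to the IMM; the Reporting paragraph sets no time limit. All SAEs go to the IRB and the CTSI monitor, again without a stated limit in that paragraph, and the CTSI monitor receives quarterly safety reports. The DSMB reviews events yearly. The CTSI monitor or DSMB may raise events that the PI has not reported. Each of these acts after the judgement.

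**The case against.** The strongest reply is that the consequence is narrow. The 7-business-day limit for unexpected SAEs carries no relatedness condition, so a reader who infers that attribution can shift serious events in general from days to a year goes further than the text allows. That stands. For most attempts and hospitalizations, being treated as expected would be enough for the annual route, whoever attributes them. That also stands, and it confines the effect to deaths and unanticipated problems.

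Second, oversight is not absent. The plan promises to report all events whether or not they are linked to participation, and several independent bodies see them. This stands too: the point is that no independent person is required at the moment of judgement, not that none ever looks.

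Third, some supporting text is easily stretched. The Data Collection paragraph of section 21.1 names the PI and IMM "with the possible alternative of the pediatric psychiatrist", but it concerns session information and the need for further action, not attribution. Section 14.1 governs re-enrolment, so it does not contradict the Reporting paragraph; it shows that the protocol already has a stricter model. It is possible, not certain, that the two raters also managed the participant.

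A reader might also infer bias in a comparison of related events between active and Unrelated-NF, or that the raters know the arm. Neither is supported: no such comparison is planned in section 18, the DSMB's list of key events is not organised by relatedness, and no visible text says what the psychiatrist or IMM knows about allocation.

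Finally, Figure 2, to which the Reporting paragraph points for decision flow, is not shown, and the DSMP is a separate document. Either may already require the IMM.

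**Conclusion.** The concern holds in this limited form. As written, the severity and attribution of an event can be determined with no independent person taking part. The clear effect on timing is for a death treated as expected, which goes from 5 business days to the annual report if judged unrelated, and for a non-serious event that would otherwise be an unanticipated problem, which goes from 10 business days to the annual report. Depending on when in the reporting year the event occurs, the annual route could mean a wait of up to about 12 months, although the CTSI monitor's quarterly reports would probably show it sooner. For unexpected SAEs there is no shift by attribution alone, only an unresolved overlap between items (3) and (6).

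This rests on three assumptions: that a death can be classed as expected, which section 16.1 suggests but no formal list confirms; that a related death follows item (2) even if expected; and that Figure 2 and the DSMP do not already make the IMM mandatory. If they do, the Reporting paragraph still needs to be aligned with them. The change is worth making because it is cheap and the monitor already has a role in the study.

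**What to change.** In section 21.1 (Reporting), replace the either/or in both sentences with the PI and the IMM, keeping the pediatric psychiatrist as adviser or third opinion, as in section 14.1. Make clear that this covers attribution of every serious event, whether or not it is classed as expected.

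Add two rules so that reporting is never delayed. If the IMM cannot be reached within the applicable window, the report goes out on time with a provisional rating that the IMM then confirms. If the PI and IMM disagree, the shorter timeline applies.

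In section 21.1 (Timeframe for Reporting), state that item (3) applies whatever the attribution, which removes the overlap with item (6). Check Figure 2 and the DSMP against the revised text.

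The cost is wording in two paragraphs, a little more IMM time and an occasional provisional rating to confirm.

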Data and Safety Monitoring Board. The PI will convene a Data and Safety Monitoring Board (**DSMB**) once a year (or ad-hoc depending on if conflicts of interests suddenly emerge). During the yearly meeting they will review AE or SAE that emerge. The DSMB includes a biostatistician, a researcher with expertise in adolescent self-injury, and a clinical psychologist. They will meet annually to 1) monitor the safety, quality and conduct of this study and 2) decide whether adequate subject safeguards are in place. The DSMB will review: 1) the progress of the proposed study, including assessments of data quality and participant recruitment, accrual and retention; 2) outcome and adverse event data to determine whether there is any change to the anticipated benefit-to-risk ratio of study participation and whether the study should continue, be changed, or terminated; 3) external factors or relevant information (e.g., pertinent scientific literature reports or therapeutic developments, results of related studies) that may have an impact on the safety of study participants or the ethics of the research study; and 4) study procedures designed to protect the privacy of the research subjects and the confidentiality of their research data. **Note that the population targeted by this study (Participants and/or patients who have attempted suicide) have a higher likelihood of a second suicide attempt, suicide completions and/or further hospitalizations. Thus, it is likely that AE or SAE will be reported for the proposed research that are not due to the research procedures but a characteristic of the population.**

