If the CTSI monitor or the DSMB notes serious and unexpected adverse events, or unanticipated problems involving risks to participants or others that have not been reported by the PI, the PI and IRB will be notified. This will be done via a letter from the CTSI monitor or the DSMB Chair/Administrator to the PI for distribution to the institutional official, sponsor (PO), and IRB. The PI will also submit an annual progress report to the IRB summarizing the data and safety monitoring activities and outlining: 1) whether participants' safety, privacy and confidentiality has been consistently assured, 2) whether research instruments have been administered in a way that protects participants' privacy, 3) progress towards recruitment goals, quality of data collection (e.g., appropriate completion of forms), and participant retention/ attrition rates, and 4) a review of new scientific literature pertinent to the safety of participants or the ethics of research participation.

If the DSMB notes reported adverse events, serious and/or unexpected adverse events, or unanticipated problems involving risks to participants or others which appear to be **related** to the research procedures during study, the PI, PO, and IRB will be notified. This will be done via a letter from the DSMB Chair/Administrator to the PI for distribution to the institutional official, sponsor NIMH PO, and the IRB after the yearly meeting. A yearly report will be made to the Data and Safety Monitoring Board (DSMB; detailed above) including all SAEs and AEs

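### The letters by which the CTSI monitor or the DSMB correct the PI's safety reporting go to the PI to pass on, with no direct copy or deadline, and the DSMB's view on relatedness waits for a yearly meeting

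*Combined protocol and SAP*

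**What the plan says.** Section 21.1, under Reporting, sets two routes for bodies outside the study team.

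The first covers serious and unexpected events or unanticipated problems "that have not been reported by the PI, the PI and IRB will be notified". The means of doing so is "a letter from the CTSI monitor or the DSMB Chair/Administrator to the PI for distribution to the institutional official", the program officer and the IRB.

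The second covers events that the DSMB thinks are related to the research procedures. The PI, the program officer and the IRB are to be told, again by a letter "to the PI for distribution to the institutional official, sponsor NIMH PO, and the IRB after the yearly meeting".

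The paragraph on the Data and Safety Monitoring Board has the PI convene the board "once a year (or ad-hoc depending on if conflicts of interests suddenly emerge", and places its review of adverse events in that yearly meeting. Timeframe for Reporting gives the PI's own limits to the IRB and NIMH:
- 3 business days for suspensions or terminations
- 5 for related deaths
- 7 for unexpected serious adverse events
- 10 for unanticipated problems
- the annual progress report for adverse events deemed expected or unrelated (item 6)

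For first-line classification, the PI takes an event "to the IMM or the Pediatric Psychiatrist and work with either of them to determine its severity and attribution".

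**The concern.** An independent check on safety reporting is worth most when the first report is missing or its classification is wrong. In the first case, the plan puts the person who did not report in charge of delivering the notice that they did not report. In the second, the board's disagreement with an unrelated call waits for a meeting held once a year.

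The second case is a realistic one here. Section 16.1 describes attempts, completed suicides and hospitalizations as features of the population rather than likely effects of the intervention, and Section 21.1 repeats the point. An expected or unrelated classification is therefore the natural default, and a second opinion on relatedness is the useful counterweight. The participants include minors at raised risk of suicide.

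**Working it through.** No sample size or power figure is involved. The check sets the routes in Section 21.1 side by side.

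| Route | From and to | Time limit stated |
|---|---|---|
| PI's own report of an unexpected serious event | PI to IRB and NIMH program officer | 7 business days |
| PI's own report of an unanticipated problem | PI to IRB and NIMH program officer | 10 business days |
| PI's own report of an event deemed expected or unrelated | PI to IRB and NIMH program officer | Annual progress report |
| Event the PI did not report, found by the CTSI monitor or DSMB | Monitor or DSMB to PI, who distributes | None |
| Event the DSMB considers related | DSMB to PI, who distributes | After the yearly meeting |

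1. *Unreported events.* The text says the IRB will be told, so the duty exists. The only mechanism described passes through the PI. The limits under Timeframe for Reporting apply to the PI's reports; none is set for the monitor's or board's letter, or for forwarding it.

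2. *Related events.* The board meets once a year and reviews events at that meeting, so the wait before its review runs from 0 to 12 months / 1 meeting = about 12 months. If events are spread evenly over the year (an assumption), the mean wait is 12 / 2 = about 6 months. An unstated forwarding time comes on top. The only stated ground for an ad-hoc meeting is a conflict of interest.

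3. *Where the wait bites.* An unexpected serious event is due from the PI in 7 business days whatever its attribution, so for that class only the board's opinion is late. An event classed as expected or unrelated falls under item 6. For that class, the board's letter and the PI's own timed report both run on a yearly cycle.

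4. *The CTSI monitor.* Research staff send the monitor safety reports quarterly. If detection rests on those reports (an assumption), a missed event could be seen within 12 / 4 = about 3 months. The resulting letter still goes to the PI.

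**The case against.** The strongest reply is that these letters sit on top of other channels, and that is correct. Section 21.1 has the PI email a signed form on the event, with its attribution, to the IRB, the program officer and the DSMB, with a copy to the independent medical monitor (IMM). CTSI monitors make regular visits, review adverse events and consult medical records for them. The section also commits to reporting all adverse events regardless of any link to the research. A suspension or termination by the DSMB must be reported within 3 business days.

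A reader might therefore infer too much in four ways:

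- That these letters are the plan's only correction for under-reporting. The channels above show otherwise.
- That a DSMB finding of relatedness can sit for a year before the IRB hears of it. The text does not say so: the long wait comes before the board's review, and the letter follows the meeting.
- That 12 months should be set against 5 to 10 business days, or turned into a count of participants trained meanwhile. Those limits govern the PI's first notice, whereas the yearly wait concerns the board's opinion. The two are not like for like.
- That the IMM is kept out. The PI may consult the psychiatrist instead at the first step, but the IMM is copied on the form.

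Figure 2 and the data safety and monitoring plan (DSMP) held in ETHOS were also not available, and either could contain a direct route.

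What the reply does not answer is the routing itself. Most of the other channels start with a report from the PI or study staff, and when the monitor or board finds a gap, the described notice goes back to the PI.

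**Conclusion.** The point holds as a weakness in a stated safety-reporting rule. For events the PI did not report, notice to the IRB and NIMH depends on the PI forwarding a letter, with no direct copy and no deadline. For events the DSMB considers related, its view can come up to about 12 months after the event, plus forwarding time. The effect is greatest for events classed as expected or unrelated.

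The 12-month figure assumes that the board meets exactly once a year, with no ad-hoc safety meeting. The conclusion applies to the protocol text as given and would soften if Figure 2 or the DSMP sets a direct route. The documents do not support calling this the plan's sole safeguard, nor saying that first notice of unexpected serious events is delayed by a year. The change should be made because it strengthens an independent check at almost no cost.

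**What to change.** In Section 21.1:

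- Under Reporting, in both paragraphs, have the CTSI monitor or the DSMB Chair send the letter directly to the IRB and the NIMH program officer, with a copy to the PI.
- Set a limit in business days, counted from the day the monitor or board notes the event. The existing limits under Timeframe for Reporting could serve.
- Remove the link to the yearly meeting from the paragraph on related events.
- Under Data and Safety Monitoring Board, add a safety trigger for ad-hoc review, such as a death or a serious adverse event that any reviewer considers possibly related.
- Bring Figure 2 and the DSMP into line with the revised text.

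The cost is wording in the protocol and the DSMP, using the same people and letters, and an occasional extra DSMB call.
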